	un tot wi	ere are 78 participants and 88 exams in the liver disease group. Within this group, usable due to using the linear probe; 5 exams are unusable because they were sc al of 10 patients had two exams – of which 5 exams were repeated since they were th the linear probe and they returned for another curved exam; another 5 were repe ey had a second biopsy performed. A total of 72 exams in the liver group have usa	reen fails. A e initially done eated becaus
	un tot	ere are 93 control patients and 95 control exams. Within the control group, 12 exa able to be used due to using the linear probe; 2 are unusable since they were scre al of 2 patients had a repeat exam since they came back after initially having an ex ear probe. A total of 79 exams in the control group have usable data.	en fails. A
	So	reen fails include those from patients who moved too much, who were too obese to age, or in whom the liver biopsy was not performed.	o obtain an
14.	ls t	here a Data Safety Monitoring (DSM) plan for this study?	
		Y No	
		Yes, a copy of the DSM report(s) for the last approval period is attached.	
		Yes, but a copy of the DSM reports(s) for the last approval period is not attac explain below.	ched. Please
15.	FD		
		A Regulated Studies Food and Drug Administration (FDA) Regulated Study, (i.e., involves drugs, N	

0 -Protoc	PROTOCOL Biomedical Research Saint Louis University	Protocol # 25138 [name]
Protocol Title:	Shear wave sonoelastography for the noninvasive evaluation of hepatic pediatric population	; fibrosis in the
a)	Have there been any changes in the FDA status of any drug or device used in the study? If yes, please explain:	
b)	Have any of the investigational drugs or devices used in this study received FDA approval? If yes, please explain:	
c)	Have any new alternative drugs or devices been approved for treatment of the study condition that may affect subjects willingness to participate? If yes, please explain:	
	Have current subjects been notified? Please explain:	
d)	Has there been a change in the standard care that may be considered as an alternative to the investigational drug or device or that would affect the original study design? If yes, please explain:	
	Have current subjects been notified? Please explain:	
e)	Is there any new information that might affect the risk/benefit ratio and the willingness of current study subjects to participate or to continue to participate in the research? If yes, please explain:	

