# PROTOCOL Biomedical Research Saint Louis University

Protocol Title:

Shear wave sonoelastography for the noninvasive evaluation of hepatic fibrosis in the pediatric population

\_\_\_\_\_

Page numbers from a sponsor's protocol/grant may be referenced in 2b and 2c.

b) List your research objectives (specific aims & hypotheses of the study).

Hypothesis: We hypothesize that shear wave sonoelastography (SWE) measurements will correlate with the histopathologic assessment of liver fibrosis in pediatric patients.

Specific Aims: To perform SWE on pediatric patients with known liver disease who undergo a liver biopsy within one month of the ultrasound exam in order to determine the accuracy of SWE in evaluating the various stages of liver fibrosis using the METAVIR histopathologic scale. As a control, we will perform SWE on patients without liver disease to establish baseline measurements in a normal liver.

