The results of the SWE using the velocity measurements displayed on the elastography map with a quantitative color map that is expressed in kPa (kiloPascals) will be correlated with the stage of fibrosis using the METAVIR scale from the liver biopsy results in order to determine the accuracy of SWE in evaluating the various degrees of liver fibrosis. The statistical analysis will include Receiver Operating Characteristic curves as well as scatter plots and box plots. The mean and median values as well as a range of the SWE measurements will be correlated with the individual METAVIR stages of fibrosis (F0-F4), and a p value will be calculated for each stage to assess the accuracy of SWE based on individual fibrosis stages. Further statistical analysis will also be performed to compare results of SWE and histopathology in subgroups of liver disease patients, such as those with NASH compared to those without. Scatter plots will be used to compare the SWE results in normal patients to those with liver disease.

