Potential subjects with known liver disease will be recruited by the pediatric gastroenterologists as these patients would be undergoing ultrasound evaluation and liver biopsy as part of standard of care treatment. These patients would be presented with a recruitment statement form during their clinic visit. During their exam in radiology, explanation of the procedure would be performed by the radiologist who would then obtain consent from the parent and informed assent from the child. Potential control patients will be recruited by giving them a recruitment statement and copy of the consent form as they check-in to the radiology department for an abdominal exam ordered by a physician as part of standard clinical care. The form will inform them that they may be asked to participate in the study following the exam. If deemed eligible by the radiologist, the radiologist will then obtain consent from the parent and informed assent from the child. Recruitment will also occur via flyers posted in the radiology department and GI clinics.

\_\_\_\_\_

\* \* \* Subject Population \* \* \*

8. Subject Population (continued) Page numbers from a sponsor's protocol/grant may be referenced in 8h.

h) Inclusion and Exclusion Criteria.

Identify inclusion criteria.

Inclusion criteria:

Test population: Any pediatric patient (0-18 years of age) with known liver disease with plans to undergo a liver biopsy within 1 month of ultrasound exam. Underlying diagnoses include but are not limited to biliary atresia, congenital fibrosis-cholestasis, Alagille syndrome, Caroli's disease, choledochal cyst, alpha-1-antitrypsin deficiency, progressive familial intrahepatic cholestasis (PFIC), viral hepatitis, glycogenosis, fructosemia, Wilson disease, cystic fibrosis, autosomal recessive polycystic kidney disease (ARPCKD), mesenterico-caval shunt, post liver transplant, and nonalcoholic steatohepatitis (NASH). Written informed consent from parent or legal guardian. Informed assent from the child.

Control population: Any pediatric patient (0-18 years of age) undergoing an abdominal ultrasound for reasons other than liver disease and in whom the US shows a normal liver, gallbladder, pancreas, spleen, and biliary tree. Written informed consent from parent or legal guardian. Informed assent from the child. In addition, the patients that have undergone biopsy and have shown no histologic evidence

Protocol Title:

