Shear wave sonoelastography for the noninvasive evaluation of hepatic fibrosis in the pediatric population

of fibrosis will also serve as a control population. The elastography measurements of these patients will be compared to those obtained in the pediatric patients without a history of liver disease in whom the ultrasound exam of the abdomen was found to be normal.

\_\_\_\_\_

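### Per-stage p values are assigned to assess SWE accuracy, which a p value cannot estimate; the planned ROC curves could, but have no METAVIR dichotomies or reported estimates

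*Combined protocol and SAP*

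**What the plan says.** The specific aim in section 2(b) is to perform SWE in children having a liver biopsy "in order to determine the accuracy of SWE in evaluating the various stages of liver fibrosis using the METAVIR histopathologic scale". The hypothesis in the same section is narrower: SWE "measurements will correlate with the histopathologic assessment of liver fibrosis in pediatric patients".

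Section 3(d) is the only analysis text. It contains three relevant statements:

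- SWE values in kPa will be correlated with METAVIR stage "in order to determine the accuracy of SWE in evaluating the various degrees of liver fibrosis".
- On methods, the section names three kinds of output: "The statistical analysis will include Receiver Operating Characteristic curves as well as scatter plots and box plots".
- Mean, median and range will be related to the individual stages F0 to F4, and "a p value will be calculated for each stage to assess the accuracy of SWE based on individual fibrosis stages".

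No test, null hypothesis or comparator is given for the per-stage p values. For the ROC curves, no grouping of stages into positive and negative is stated. Nor is there a commitment to report an AUROC, a sensitivity, a specificity, a kPa cut-off or a confidence interval.

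**The concern.** The plan gives the p value the task of measuring accuracy. A p value answers a different question, namely whether the data are compatible with no association. Its size reflects both how well SWE separates the groups and how many patients are in them. Two stages with the same discrimination can give different p values, and two with different discrimination can give the same one. Without a named test and comparator, the quantity is not even defined.

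This bears on the study's purpose. Section 10(a) argues that, if SWE proves accurate, fewer children, or none, may need a liver biopsy. Judging that claim requires the proportion of children at a given stage whom SWE would miss or over-call at a stated cut-off, and the uncertainty of those proportions. A set of significant per-stage p values supplies neither. Leaving the ROC groupings and cut-off rule open after the data are in also allows them to be chosen because they look favourable.

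**Working it through.** **Is there a planned figure to reproduce?** No. Section 2(c) gives 100 test patients as the minimum to determine accuracy, but names no accuracy parameter, precision target, alpha or power. That number can be neither reproduced nor refuted, and this point does not depend on it.

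**Inputs.** The number of liver exams comes from Continuing Review item 13: "A total of 72 exams in the liver group have" usable data (the line is cut off in the text; the matching sentence for controls is complete). The stage mix is not in the documents. The splits (36/36, 14/58, 7/65) and the AUROCs are therefore assumptions. They are generic two-group splits, not the plan's per-stage comparisons, which are undefined. Exams are treated as independent. Item 13 reports five patients examined again because of a second biopsy, so that holds only approximately.

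**Formulas.**

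- Rank-sum test of AUROC = 0.5: z = (AUROC − 0.5) / √[(n1 + n2 + 1) / (12·n1·n2)], two-sided p.
- Hanley–McNeil SE: √{[A(1−A) + (n1−1)(Q1−A²) + (n2−1)(Q2−A²)] / (n1·n2)}, with A the AUROC, Q1 = A/(2−A) and Q2 = 2A²/(1+A). The 95% CI is A ± 1.96·SE.

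**Step 1: null standard errors.** 36/36: √(73/15,552) = 0.0685. 14/58: √(73/9,744) = 0.0866. 7/65: √(73/5,460) = 0.1156.

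**Step 2: same discrimination, different p.** At AUROC 0.65 the numerator is 0.15.

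| Split | z | p |
|---|---|---|
| 36/36 | 2.189 | 0.029 |
| 14/58 | 1.733 | 0.083 |
| 7/65 | 1.297 | 0.19 |

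Only the group sizes changed.

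**Step 3: different discrimination, nearly the same p.** AUROC 0.75 at 7/65 gives z = 0.25/0.1156 = 2.162 and p = 0.031. That is close to the 0.029 from AUROC 0.65 at 36/36.

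**Step 4: significance hides imprecision.** At AUROC 0.85, Q1 = 0.85/1.15 = 0.7391, Q2 = 1.445/1.85 = 0.7811, A² = 0.7225 and A(1−A) = 0.1275.

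| Split | z | p | SE | 95% CI |
|---|---|---|---|---|
| 36/36 | 5.109 | below 0.000001 | 0.0461 | 0.76–0.94 |
| 14/58 | 4.044 | 0.00005 | 0.0673 | 0.72–0.98 |
| 7/65 | 3.027 | 0.0025 | 0.0935 | 0.67–1.00 (1.03 before capping) |

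Every split is significant, but the last is compatible with anything from modest to perfect discrimination.

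**The case against.** The strongest reply is that the right tool is already in the plan. A ROC curve displays sensitivity against 1 − specificity over all cut-offs. With a five-level reference it cannot be drawn without grouping the stages, so an AUROC at some grouping is arguably implied. The correlation is also planned expressly to determine accuracy. This largely stands. A reader might infer that accuracy rests on the p values alone, and section 3(d) does not support that. What remains is that a specific stage-level accuracy role is given to the p value, and that the ROC analysis lacks its groupings, estimates and cut-off rule.

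A second reply is that the figures show only the general fact that p depends on n. That is fair. They illustrate the mechanism and do not predict this study's results.

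A reader might also infer that each stage will be tested against all other stages, so that a middle stage such as F2 would look uninformative even with a good marker. The documents do not say this. Section 8(h) offers two other references: controls "in whom the US shows a normal liver, gallbladder, pancreas, spleen, and biliary tree", and biopsied patients without histologic evidence "of fibrosis will also serve as a control population". The problem would not arise against either.

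Finally, no decision about a participant depends on this text, and only data analysis remains (Continuing Review item 1; Expedited Paragraphs, category 8(c)). That limits the severity, but it also means the analysis is the part that can still be corrected.

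**Conclusion.** The point holds in this form: the per-stage p value is given a task it cannot perform, and the ROC analysis that could perform it is under-specified. It should be fixed.

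That a p value does not estimate accuracy needs no assumption. The size of the effect does. Under the assumed splits of 72 exams, p moves from 0.029 to 0.19 at a fixed AUROC of 0.65, and the interval around an AUROC of 0.85 roughly doubles in standard error (0.0461 to 0.0935) while remaining significant. The true stage mix and AUROCs are unknown from the documents.

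Two further inferences should not be drawn. Over-optimism from choosing a cut-off in the same data is not a defect of section 3(d), which proposes no cut-off; it is a hazard of the remedy. Nor can one say that AUROCs or cut-offs have never been reported: section 16 lists a meeting submission with a table and figures from December 2016, whose content is not available here.

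**What to change.** Revise section 3(d) as follows.

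1. Do not present per-stage p values as accuracy. If an individual-stage comparison is kept, name its test and comparator.
2. Make the planned ROC analysis the accuracy measure, at F1 or higher, F2 or higher, F3 or higher, and F4. Restrict it to biopsied patients, because controls enrolled on a normal ultrasound have no METAVIR stage.
3. At each threshold report AUROC with 95% CI, and sensitivity and specificity with 95% CIs at a kPa cut-off chosen by a stated rule.
4. Because the cut-off is derived and evaluated in the same exams, report an internally validated, optimism-corrected estimate, resampling patients rather than exams because of the repeat biopsies. Otherwise label the cut-offs exploratory.
5. Test the correlation hypothesis of section 2(b) once, with a rank correlation or ordinal trend test. Keep stage-wise mean, median and range as descriptive.
6. Label the analysis as specified after data collection.

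**Cost.** No new patients or measurements are needed. Prespecification cannot be recovered, and intervals will be wide at sparse thresholds. Optimism correction is only partial. In a simulation with equal-variance normal groups, AUROC 0.85 and a Youden cut-off, apparent, corrected and true sensitivity were 0.817, 0.787 and 0.772 at 36/36; 0.836, 0.779 and 0.740 at 14/58; and 0.867, 0.778 and 0.713 at 7/65. The share of optimism removed is 0.030/0.045 = 67%, 0.057/0.096 = 59% and 0.089/0.154 = 58%.

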#### Please save frequently

c) Describe the study design (e.g., single/double blind, parallel, crossover, control, experimental, observational, etc.). If the study is investigator-initiated, a timeline for individual subject recruitment, follow-up, and analysis for the study is required. Also, indicate if the subjects will be randomized.

The study design is a prospective single blind control experiment. Subject recruitment will be ongoing as patients who undergo routine liver biopsy in order to evaluate their liver disease will also undergo an ultrasound with sonoelastography. The minimum number of patients required in the test group in order to determine accuracy of the research test is 100. Study recruitment for patients without liver disease will be stopped once 100 patients are enrolled. An additional 8 months will be required for study analysis.

d) If subjects will be given placebo, please justify placebo use. \*?HELP?\*

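### The normal-versus-liver-disease SWE comparison rests on scatter plots, which give neither a baseline value nor a difference with its uncertainty

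*Combined protocol and SAP*

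**What the plan says.** Section 2(b) gives the controls a purpose: "As a control, we will perform SWE on patients without liver disease to establish baseline measurements in a normal liver". Section 2(c) sets their number without a derivation: "Study recruitment for patients without liver disease will be stopped once 100 patients are enrolled".

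Section 3(d) then describes the analysis:

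- A general list that names no patient group: "The statistical analysis will include Receiver Operating Characteristic curves as well as scatter plots and box plots".
- Stage summaries: "The mean and median values as well as a range of the SWE measurements will be correlated with the individual METAVIR stages" (F0-F4). A p value is promised for each stage; its comparator is not stated.
- Further analysis within subgroups of liver-disease patients, such as NASH versus not.
- The control contrast: "Scatter plots will be used to compare the SWE results in normal patients to those with liver disease".

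Section 8(h) defines the controls as "Any pediatric patient (0-18 years of age) undergoing an abdominal ultrasound" for reasons other than liver disease, with a normal scan. The test group is "Any pediatric patient (0-18 years of age) with known liver disease" and a planned biopsy. Both span the same ages, and no matching is described. The section adds a second control set: biopsied patients with no histological sign "of fibrosis will also serve as a control population". Their measurements are to be compared with those of the normal controls, but no statistic is named.

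Section 11(c) lists age and gender among the data taken from the record. No analysis is said to use them. A confidence interval is not mentioned anywhere in the document.

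**The concern.** Establishing a normal-liver baseline is a stated aim, and by the continuing-review count (item 13) controls are 93 of 171 patients. The one method attached to them is a graph. It shows the overlap between groups, but it states no baseline value, no size of difference and no uncertainty for either. The results could therefore describe normal livers, and how far diseased livers depart from them, by eye alone.

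The second control comparison has the same gap: it is promised without a statistic. Finally, the two groups are unmatched over the whole of childhood. If SWE varied with age and the groups differed in age, a raw contrast would mix the two effects. Age is already recorded, so this can be handled.

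**Working it through.** **Which method reaches which group**

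| Group or contrast | Named in the plan | Estimate with CI |
|---|---|---|
| Biopsied patients, by METAVIR stage | mean, median, range, p value per stage (3(d)) | no CI named |
| Ultrasound-normal controls alone | nothing specific; the general list may apply | none named |
| Normal versus liver disease | scatter plot (3(d)) | none named |
| Biopsied no-fibrosis versus normal | to be compared (8(h)) | none named |

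The normal controls are defined by a normal scan, so they have no METAVIR stage and the stage summaries do not cover them. Section 3(b) says the mean value will be used, but that is the mean of one patient's ten acquisitions, not a group estimate.

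**No planned figure to reproduce.** The 100 controls come with no SD, effect size, power or precision target. What can be computed is the precision that the collected data would give. Results are in SD units because no SD is stated.

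Inputs from continuing review item 13: 79 usable control exams, 72 usable liver exams, 93 control and 78 liver patients, and 5 liver patients re-examined because of a second biopsy.

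1. Share of controls: 93/(93+78) = 93/171 = 54%.
2. Control mean, 95% CI half-width, t(n-1)/sqrt(n): n = 79 gives 0.224 SD. At the planned n = 100 it would be 0.198 SD.
3. Overall difference, common SD, t × sqrt(1/n1 + 1/n2): 72 versus 79 gives 0.322 SD.
4. One exam per liver patient: 72 - 5 = 67, assuming both exams of those 5 patients are usable. 67 versus 79 gives 0.328 SD.
5. Unequal spread. A mixed F0-F4 group may vary more than controls. With liver SD assumed at 1, 1.5 and 2 times the control SD, the Welch half-width for 67 versus 79 is 0.328, 0.426 and 0.534 control SDs.
6. No-fibrosis versus controls, common SD. The F0 count is not given. At an assumed 10 or 20 patients against 79, the half-width is 0.667 or 0.497 SD. Any other stage of that size would have the same precision.
7. A 95% reference limit in controls, 1.96 × sqrt(1/n + 1.96²/(2(n-1))): 0.378 SD at n = 79. In age bands of 20 or 26 it is 0.76 or 0.67 SD.
8. Cost of age adjustment. For roughly equal groups whose mean ages differ by d age SDs, the squared correlation of group with age is d²/(d²+4), so the CI widens by sqrt(1 + d²/4). For d = 0, 0.5 and 1 (assumed) the factor is 1.00, 1.03 and 1.12, before any gain from variance that age explains.

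Items 2 to 7 show what the data could deliver. They do not measure harm done by the present wording.

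**The case against.** The strongest reply is that the plan already offers more than a scatter plot. The sentence listing ROC curves and box plots is not limited to biopsied patients, and a box plot of controls would show a median and quartiles. The no-fibrosis patients, one of the two declared control sets, fall in F0 and so have a named mean, median and range. The p value for each stage might use normal controls as comparator. All this stands, so a reader who infers that controls will have no numerical summary at all goes further than the text allows. What remains is that none of these is tied to the normal controls, and none gives an estimated difference with an interval.

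It is also fair to say that this is not the main question. The hypothesis in section 2(b) concerns SWE against histology, and normal patients enter as a control.

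A reader might further infer that age confounds the contrast. The documents do not support that: they give no age gap between groups and no relation of SWE to age. A shared 0-18 range and a recorded age make adjustment sensible, but they do not show bias. Nothing in the documents calls for sex adjustment in particular.

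Lastly, an overall normal-versus-disease difference depends on which stages happened to be biopsied. That is correct, and it is why stage-specific differences are preferable.

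**Conclusion.** The point holds as a minor to secondary one. A stated graphics-only comparison should be supplemented by estimated differences with 95% CIs, and the normal-liver aim needs a reported value. The second control comparison in section 8(h) needs a named statistic.

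Usable precision is available from data in hand: about 0.22 SD for the control mean and 0.32 to 0.33 SD for the overall difference, assuming independence and a common SD. The latter rises to 0.53 control SDs if the liver group is twice as variable. A stage of 10 to 20 patients would give 0.67 to 0.50 SD against controls. The SD ratio and stage counts are assumptions.

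No size is claimed for age confounding, which is unknown. It would also be wrong to infer that the accuracy results are compromised: the biopsy-based ROC and stage analyses do not depend on this contrast.

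**What to change.** Keep the scatter plot and add to section 3(d):

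1. For ultrasound-normal controls, the SWE mean or median with 95% CI and a range, described by age. Age bands should not be fine, since limits in bands of 20 to 26 carry about ±0.7 SD.
2. The difference between controls and each METAVIR stage, and liver disease overall, from a regression adjusted for age, with 95% CIs. Use one exam per patient or patient-clustered errors, and allow unequal variances. State that the overall figure depends on the stage mix. Sex adjustment is optional.
3. The difference between biopsied no-fibrosis patients and normal controls with 95% CI, keeping the two control sets separate.

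No new patients, visits or variables are needed. The costs are slightly more analysis work and a CI up to about 12% wider if mean ages differ by 1 age SD (assumed). A post hoc label may also be needed: the continuing review says only data analysis remains, and section 16 lists a meeting submission dated 12/09/2016 whose content is not visible. If results had been seen before these analyses were specified, they should be labelled post hoc.
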